9.2 Sample Size

This study will include as many eligible subjects as are willing to participate; however, site criteria must be met.

Given a continuous enrollment design, the study will include two enrollment milestones over the 2-year study period. Milestone 1, at the end of year 1 will be to recruit 750 subjects. Milestone 2, at the end of year 2, will be recruit 750 subjects. Together, recruitment milestones result in enrolling a total of up to 1500 subjects.

The number of subjects may vary based on the real-life use of ST products. Sites will be recruited from countries where ST products are available: Canada, United Kingdom, Germany, and Australia. Sites from additional countries may be included as ST products become available in those countries.

The present study has an observational design that poses low-burden for subjects, as the number and frequency of in-clinic (telemedicine) visits represent those necessary for adequate monitoring of treatment for chronic pain and at-home follow-ups will be completed using a simple online app and take no longer than 15 minutes to complete. On this premise, we did not restrict the sample size based on an estimated minimum required sample. Furthermore, the observational nature of the primary endpoint (daily average dose [in mg] of THC and CBD and mode of administration [inhaled or ingested]), did not permit a statistical calculation of a sample size. A sample size of up to 1500 subjects is consistent with similar previous observational registry studies.

9.3 Handling of Dropouts, Missing Data

For descriptive summaries of data, there will be no imputation for missing data, unless otherwise stated. All data collected prior to a subject withdrawing will be listed and included in data summaries.

For analyses involving linear mixed effects modeling, data points that are missing due to participant dropout will be handled assuming that data are missing at random (MAR) conditional on observed information, which is less restrictive than missing completely at random assumed in fixed effects analyses such as ANCOVA. In this procedure, all available cases, including those with missing information, will be included in the analyses using full information maximum likelihood estimation. This procedure increases power and reduces bias in parameter estimation.

9.4 Statistical Software

Data manipulation, tabulation of descriptive statistics, calculation of inferential statistics, and graphical representations will be performed using R (version 4.0 or higher)³¹ or the SuperMix statistical software. Mixed effects models of continuous outcomes will be conducted using the nlme³² and/or lme4³³ packages, mixed effects models of ordinal outcomes with the mixor³⁴ or ordinal³⁵ package, mixed effects models of binomial outcomes using the lme4 package³³, and mixed effects hurdle regression models with the GLMMadaptive package³⁶.

If the use of other software is warranted, the final clinical study report will detail what software was used and for what purposes.

10. ETHICS

10.1 Ethical Conduct of the Study

The study will be conducted consistent with consensus ethics principles derived from international ethics guidelines including the ICH GCP, the Declaration of Helsinki, and applicable local regulatory requirements and laws. The registry will only launch after receiving ethical approval from the Canadian SHIELD ethics review board and approval will be renewed on a yearly basis.

Any site that joins the registry will provide additional ethics approval as required by their local regulatory bodies as part of the feasibility evaluation. Canopy Growth will review all outside ethics approvals and only sites with ethical approval will receive a contract and invitation to the investigator training.

10.2 Subject Information and Consent

Informed consent will be obtained prior to the subject participation in any study activities. Prior to obtaining consent, the site physician will ensure that:

- The potential subject has had a discussion with an individual knowledgeable about the research, including the nature and objectives of the study and possible risks associated with participation.
- The potential subject is given a copy of written material (e.g., consent documents, Spectrum Therapeutics leaflet) that has received prior approval by the appropriate ethics committee(s) and meets local regulatory and legal requirements.
- The potential subject has ample opportunity to ask questions about the study.
- An assessment of capacity has taken place. For consent to be ethical and lawfully valid, subjects in this study must be capable of providing informed consent for their participation. A capable person will:
 - Understand the purpose and nature of the research.
 - Understand what the research involves, its benefits (or lack of benefits), risks, and burdens.
 - Understand how their interests and privacy are protected.
 - Understand the alternatives to participation.
 - Be able to retain the information long enough to make an effective decision.
 - Be able to make a free choice.
 - Be capable of making this particular decision at the time it needs to be made.

11. STUDY TERMINATION

The Sponsor reserves the right to terminate the participation of either an individual site or the study at any time, for any reason, including, but not limited to, the following:

- The information on the product leads to doubt as to the benefit/risk ratio.
- Recommendation of the Scientific Committee.
- Subject enrollment is unsatisfactory.
- Noncompliance of the site physician, delegated staff with any provision of the study protocol, and breach of the applicable laws and regulations.

As directed by the Sponsor, site physicians will be notified and required to inform local ethics committees and all study subjects of study termination.

Local ethics committees or regulatory authorities may also decide to stop the study, part of the study, or a study site at any time.

12. PUBLICATION POLICY

The information obtained during the conduct of this study is considered confidential. It may be used by, or on behalf of the Sponsor for regulatory purposes as well as for the general development of ST medical cannabis products. All information supplied by the Sponsor in connection with this study shall remain the sole property of the Sponsor and is to be considered confidential information.

The site physicians will not disseminate any publication or release pertaining to the study and/or results of the study without the Sponsor's express written consent; the Sponsor will not unreasonably withhold its approval. For example, withholding approval for publication will be deemed unreasonable if such a decision is based exclusively on the fact that the results of the study are negative or equivocal. In contrast, withholding approval will be deemed reasonable if the validity of the study methodology or results are in question. Different parts of the study may be published separately.

14. APPENDICES

Appendix 1- PHYSICIAN-VERIFIED BASELINE ASSESSMENT

Baseline Interview

Invite Confirmation

Before continuing with this form, please ensure you have invited the patient to create their own account with RedCapCloud.

As a reminder, this is done by clicking the three horizontal lines beside their 'Subject Number' in the table found in the 'Consent' section of 'Subjects'.

Please use an email address the patient has access to.

Has an invite already been sent to the patient's email?

- Yes
 No

Demographics

Date of clinic visit (enrollment into registry)

(YYYY-MM-DD)

Country of residence

- Australia
 Canada
 Germany
 United Kingdom

Province or Territory of residence

- Alberta
 British Columbia
 Manitoba
 New Brunswick
 Newfoundland & Labrador
 Northwest Territories
 Nova Scotia
 Nunavut
 Ontario
 Prince Edward Island
 Quebec
 Saskatchewan
 Yukon

State of residence

- Baden-Württemberg
- Bavaria
- Berlin
- Brandenburg
- Bremen
- Hamburg
- Hesse
- Lower Saxony
- Mecklenburg-Vorpommern
- North Rhine- Westphalia
- Rhineland-Palatinate
- Saarland
- Saxony
- Saxony-Anhalt
- Schleswig-Holstein
- Thuringia

State of residence

- New South Wales
- Queensland
- South Australia
- Tasmania
- Victoria
- Western Australia

Age at date of enrollment

Sex assigned at birth

- Female
- Male
- Prefer not to answer

Gender identity

- Female
- Male
- Transgender
- Gender non-conforming
- Prefer not to answer

Racial identity

- Aboriginal (e.g. Inuit)
- Arab / West Asian (e.g. Armenian)
- Black (e.g. African)
- East Asian (e.g. Chinese)
- Latin American (e.g. Brazilian)
- South Asian (e.g. Indian)
- Southeast Asian (e.g. Burmese)
- White (e.g. Caucasian)
- Prefer not to answer

Current employment status

- Full-time
- Part-time (unrelated to medical status)
- Part-time / Reduced Hours (due to medical status)
- Student
- Short-term disability (3 months or less)
- Long-term disability (more than 3 months)
- Retired
- Unemployed (unrelated to medical status)
- Unemployed (due to medical status)

Length of short-term disability (in months)

Length of long-term disability (in months)

BMI

Patient's current height (cm)

Patient's current weight (kg)

Patient's calculated BMI

Chronic Pain Classification

Patients classification of chronic pain (Top Level diagnosis)

- Chronic Primary Pain
- Chronic Post-surgical / Post-traumatic Pain
- Chronic Neuropathic Pain

- Irritability
- Stress

Please indicate the type of sleep disruption that best describes that which is the primary focus of the patient's primary treatment goal

- Increase daytime alertness
- Increase sleep quality or quantity

Please indicate the type of function that best describes that which is the primary focus of the patient's primary treatment goal

- Activities unrelated to employment (e.g. leisure activities)
- Employment related activities (e.g. return to work full time)
- Improve relationships

Concomitant medication

Is your patient currently taking an of the following classes of prescription medication (select all that apply)

- Nonsteroidal Anti-inflammatory Drugs (NSAIDs) and Acetaminophen
- Antidepressants (TCA, SNRI, SSRI)
- Anticonvulsants (gabapentin, pregabalin)
- Muscle Relaxants
- Benzodiazepines
- Opioids
- Other
- Medical Cannabis from a Licensed Producer other than Spectrum

NSAIDs and Acetaminophen Dosing Information

Name of drug

Daily dose of [baseline_visit][nsaid1_name] (total mg per day)

- Check to add additional NSAID /Acetaminophen medications

Name of drug

Daily dose of [baseline_visit][nsaid2_name] (total mg per day)

- Check to add additional NSAID /Acetaminophen medications

Name of drug

Daily dose of [baseline_visit][nsaid3_name] (total mg per day)

Antidepressants Dosing Information

Name of drug

Daily dose of [baseline_visit][antidep1_name](total mg per day)

Check to add additional Antidepressant medications

Name of drug

Daily dose of [baseline_visit][antidep2_name] (total mg per day)

Check to add additional Antidepressant medications

Name of drug

Daily dose of [baseline_visit][antidep3_name] (total mg per day)

Anticonvulsants Dosing Information

Name of drug

Daily dose of [baseline_visit][anticon1_name] (total mg per day)

Check to add additional anticonvulsant medications

Name of drug

Daily dose of [baseline_visit][anticon2_name] (total mg per day)

Check to add additional anticonvulsant medications

Name of drug

Daily dose of [baseline_visit][anticonvu3_name] (total mg per day)

Muscle Relaxants Dosing Information

Name of drug _____

Daily dose of [baseline_visit][musrel1_name] (total mg per day) _____

Check to add additional muscle relaxant medications

Name of drug _____

Daily dose of [baseline_visit][musrel2_name] (total mg per day) _____

Check to add additional muscle relaxant medications

Name of drug _____

Daily dose of [baseline_visit][musrel3_name] (total mg per day) _____

Benzodiazepines Dosing Information

Name of drug _____

Daily dose of [baseline_visit][benzo1_name](total mg per day) _____

Check to add additional benzodiazepine medications

Name of drug _____

Daily dose of [baseline_visit][benzo2_name] (total mg per day) _____

Check to add additional benzodiazepine medications

Name of drug _____

Daily dose of [baseline_visit][benzo3_name] (total mg per day) _____

Opioid Dosing Information

Please enter MME (total daily morphine equivalent dose in mg) _____

Other Medication Information

Please indicate name of other drugs not included in the above classes _____

Daily dose (total mg per day), if available _____

ST Regimen Canada

[figure not shown]

Please enter in the table below total daily amount of Spectrum Therapeutics products consumed. Please be conscious of the units provided:

Inhaled cannabis = total number of inhalations per day

Ingested oils = total mL per day

Spray format = total number of sprays per day

Capsules & edibles = total number of capsules or total number of chocolate bar squares per day

	Inhaled Formats (dried flower, extract vaporizers) -- report daily total number of inhalations	Ingested Oil Formats - report daily total number of mLs	Spray Formats - report daily total number of sprays	Low Potency Capsule & Edible Formats - report daily total number of low-potency capsules (i.e. 2.5 mg), number of chocolate bar squares, etc.	High Potency Capsule Formats - report daily total number of high-potency capsules
Red (examples include Spectrum #1-4; Tweed Bakerstreet, Highlands, Houdstooth, Donegal; LBS Sunset)	 inhalations  	 mL  	 sprays  	 capsules  	 capsules  
Orange	 inhalations  		 sprays  		
Purple (examples include LBS Ocean View)	 inhalations  		 sprays  		
Blue (examples include Tweed Penelope)	 inhalations  	 mL  	 sprays  	 capsules  	 capsules  
Green (examples include Tweed Argyle)	 inhalations  	 mL  	 sprays  	 capsules  	 capsules  
Yellow (examples include Tweed CBD Softgels)	 inhalations  	 mL  	 sprays  	 capsules  	 capsules  
Spectrum Clear (or White)		 mL  			

You indicated that your patient has been recommended an inhaled format. Please identify their most common method of administration.

(inhal_admin)

[Branching logic exists]

- Smoked
- Dried flower vaporizer (e.g. Stroz and Bickel, PAX)
- Extract vaporizer (e.g. vape pen cartridge)

Do you or your patient know the temperature set point of the vaporizer (in °C)

(inhal_vape_Y/N)

[Branching logic exists]

- Yes
- No

If known, please provide the temperature set point of your patient's vaporizer (in °C) _____

(inhal_vape_temp)

(125 / 300)

[Branching logic exists]

Calculated, approximated total daily dose of THC and CBD (in mgs)

	THC	CBD
Inhaled	
(inhal_THC)
  
View Equation
	
(inhal_CBD)
  
View Equation

Ingested	
(ingest_THC)
  
View Equation
	
(ingest_CBD)
  
View Equation

Patient reported outcomes

BPI

Throughout our lives, most of us have had pain from time to time (such as minor headaches, sprains, and toothaches). Have you had pain other than these everyday kinds of pain today?

- Yes
- No

Please select the number (0= no pain, 10= pain as bad as you can imagine) that best describes your pain at its worst in the last 24 hours.

- 0
- 1
- 2
- 3
- 4
- 5
- 6
- 7
- 8
- 9
- 10

Please select the number (0= no pain, 10= pain as bad as you can imagine) that best describes your pain at its least in the last 24 hours.

- 0
- 1
- 2
- 3
- 4
- 5
- 6
- 7
- 8
- 9
- 10

Please select the number (0= no pain, 10= pain as bad as you can imagine) that best describes your pain on the average.

- 0
- 1
- 2
- 3
- 4
- 5
- 6
- 7
- 8
- 9
- 10

Please select the number (0= no pain, 10= pain as bad as you can imagine) that best describes how much pain you have right now.

- 0
- 1
- 2
- 3
- 4
- 5
- 6
- 7
- 8
- 9
- 10

Please select the number (0= does not interfere, 10= completely interferes) that best describes how, during the past 24 hours, pain has interfered with your: **General Activity**

- 0
- 1
- 2
- 3
- 4
- 5
- 6
- 7
- 8
- 9
- 10

Please select the number (0= does not interfere, 10= completely interferes) that best describes how, during the past 24 hours, pain has interfered with your: **Mood**

- 0
- 1
- 2
- 3
- 4
- 5
- 6
- 7
- 8
- 9
- 10

Please select the number (0= does not interfere, 10= completely interferes) that best describes how, during the past 24 hours, pain has interfered with your: **Walking ability**

- 0
- 1
- 2
- 3
- 4
- 5
- 6
- 7
- 8
- 9
- 10

Please select the number (0= does not interfere, 10= completely interferes) that best describes how, during the past 24 hours, pain has interfered with your: **Normal work (includes both work outside the home and housework)**

- 0
- 1
- 2
- 3
- 4
- 5
- 6
- 7
- 8
- 9
- 10

Please select the number (0= does not interfere, 10= completely interferes) that best describes how during the past 24 hours, pain has interfered with your: **Relations with other people**

- 0
- 1
- 2
- 3
- 4
- 5
- 6
- 7
- 8
- 9
- 10

Please select the number (0= does not interfere, 10= completely interferes) that best describes how during the past 24 hours, pain has interfered with your: **Sleep**

- 0
- 1
- 2
- 3
- 4
- 5
- 6
- 7
- 8
- 9
- 10

Please select the number (0= does not interfere, 10= completely interferes) that best describes how during the past 24 hours, pain has interfered with your: **Enjoyment of life**

- 0
- 1
- 2
- 3
- 4
- 5
- 6
- 7
- 8
- 9
- 10

EQ5D

Mobility

- I have no problems in walking about
- I have slight problems in walking about
- I have moderate problems in walking about
- I have severe problems in walking about
- I am unable to walk

Self-Care

- I have no problems washing or dressing myself
- I have slight problems washing or dressing myself
- I have moderate problems washing or dressing myself
- I have severe problems washing or dressing myself
- I am unable to wash or dress myself

Usual Activities

- I have no problems doing my usual activities
- I have slight problems doing my usual activities
- I have moderate problems doing my usual activities
- I have severe problems doing my usual activities
- I am unable to do my usual activities

Pain/Discomfort

- I have no pain or discomfort
- I have slight pain or discomfort
- I have moderate pain or discomfort
- I have severe pain or discomfort
- I have extreme pain or discomfort

Anxiety/Depression

- I am not anxious or depressed
- I am slightly anxious or depressed
- I am moderately anxious or depressed
- I am severely anxious or depressed
- I am extremely anxious or depressed

We would like to know how good or bad your health is TODAY. Please write a number between 0 and 100.

100 means the best health you can imagine

0 means the worst health you can imagine

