7. OUTCOME ASSESSMENTS

7.1 Study Endpoints

Primary endpoints

- Physician selection of Spectrum Therapeutics (ST) medical cannabis treatment regimen and changes over time in:
 - (1) average daily dose of THC and CBD (in mg);
 - (2) route of administration (inhaled or ingested).

Secondary endpoints

- Subject selection of ST treatment regimen and changes over time in:
 - (1) average daily dose of THC and CBD (in mg);
 - (2) route of administration (inhaled or ingested).
- Change in BPI-SF responses from baseline.
- Change in EQ5D-5L responses from baseline.
- PGI-C for the target treatment goal.
- CGI-I for the target treatment goal.
- In subjects taking an opioid, changes in opioid use over time (calculated as milligram morphine equivalents [MME]/day).
- Among subjects taking other medication, total daily dose change over time.

Safety endpoint

- Incidence of AEs stratified by product and formulation.

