7.2.6 Other Concomitant Medications

Physicians will confirm subjects who take any non-opioid concomitant medication for pain at baseline, or who start it during the study, and will be asked to report the medication type. The following medication categories have been identified as common medication classes taken by chronic pain patients: Nonsteroidal Anti-inflammatory Drugs (NSAIDs) and Acetaminophen, Antidepressants, Anticonvulsants, Benzodiazepines and Muscle Relaxants. Physicians will be asked to report the medication type and total daily dose, and any changes throughout the study.

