Do you or your patient know the temperature set point of the vaporizer (in °C)
(*inhal_vape_Y/N*)
[Branching logic exists]

- Yes
 No

If known, please provide the temperature set point of your patient's vaporizer (in °C) _____
(*inhal_vape_temp*)
(125 / 300)
[Branching logic exists]

Calculated, approximated total daily dose of THC and CBD (in mgs)

	THC	CBD
Inhaled	(inhal_THC)  View Equation	(inhal_CBD)  View Equation
Ingested	(ingest_THC)  View Equation	(ingest_CBD)  View Equation

Concomitant medication

Concomitant medication - Existing

Existing NSAIDs and Acetaminophen Dosing Information

At last visit, you indicated that your patient was taking [baseline_visit][nsaid1_name]. Is your patient still taking this medication?

- Yes
 No

What is their current daily dose of [baseline_visit][nsaid1_name] (total mg per day)?

Please select the reason why your patient stopped taking this medication.

- Side effects
 Cost
 Lack of benefit
 No longer needs/ replaced by medical cannabis
 Unknown

At last visit, you indicated that your patient was taking [baseline_visit][nsaid2_name]. Is your patient still taking this medication?

- Yes
 No

Please select the reason why your patient stopped taking this medication.

- Side effects
 Cost
 Lack of benefit
 No longer needs/ replaced by medical cannabis
 Unknown

What is their current daily dose of [baseline_visit][nsaid2_name] (total mg per day)?

At last visit, you indicated that your patient was taking [baseline_visit][nsaid3_name]. Is your patient still taking this medication?

- Yes
 No

Please select the reason why your patient stopped taking this medication.

- Side effects
- Cost
- Lack of benefit
- No longer needs/ replaced by medical cannabis
- Unknown

What is their current daily dose of [baseline_visit] [nsaid3_name] (total mg per day)?

Existing Antidepressants Dosing Information

At last visit, you indicated that your patient was taking [baseline_visit][antidep1_name]. Is your patient still taking this medication?

- Yes
- No

Please select the reason why your patient stopped taking this medication.

- Side effects
- Cost
- Lack of benefit
- No longer needs/ replaced by medical cannabis
- Unknown

What is their current daily dose of [baseline_visit] [antidep1_name] (total mg per day)?

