- No longer needs/ replaced by medical cannabis
- Unknown

What is their current MME?

Existing Other Medications Dosing Information

At last visit, you indicated that your patient was taking other medications, including [baseline_visit][othmed_name]. Is your patient still taking any of these other prescription medications?

- Yes
- No

Please describe any **changes** to their other existing prescription medications since last visit (including changes to total daily dose)

Concomitant Medications - New

Since last visit, has your patient **started** taking any of the following classes of prescription medication (select all that apply)

- Nonsteroidal Anti-inflammatory Drugs (NSAIDs) and Acetaminophen
- Antidepressants (TCA, SNRI, SSRI)
- Anticonvulsants (gabapentin, pregabalin)
- Muscle Relaxants
- Benzodiazepines
- Opioids
- Other
- Medical Cannabis from a Licensed Producer other than Spectrum

Name of new NSAID/Acetaminophen medication (started since last visit)

Daily dose of [physician_1st_follow][nsaid4_name] (total mg per day)

Name of new antidepressant medication (started since last visit)

Daily dose of [physician_1st_follow][antidep4_name] (total mg per day)

Name of new anticonvulsant medication (started since last visit)

Daily dose of [physician_1st_follow][anticon4_name] (total mg per day)

Name of new muscle relaxant medication (started since last visit)

Daily dose of [physician_1st_follow][musrel4_name] (total mg per day)

Name of new benzodiazepine medication (started since last visit)

Daily dose of [physician_1st_follow][benzo4_name] (total mg per day)

Please enter MME (total daily morphine equivalent dose in mg)

Name of new prescription medication (started since last visit, not covered in above classes)

Daily dose of [physician_1st_follow][othmed4_name] (total mg per day)

Physician AE form

Product information

Do you have any adverse events to report related to this patient?

- Yes
- No

Suspect product(s) name

Start date

_____ (YYYY-MM-DD)

End date

_____ (YYYY-MM-DD)

Route of administration

- oral - oil
- oral - softgel
- oral - spray
- oral - beverage
- oral - chocolate
- oral
- inhalation - smoked
- inhalation - vaporized
- inhalation

Dose (please include amount and unit i.e. mg, ml, #softgels, #inhalations, etc.)

Did reaction disappear after reducing the dose or stopping the product ?

- No
- Yes
- Unknown

Did reaction reappear after same product/treatment was restarted?

- No
- Yes
- Unknown

AE description

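### Section 7.2.6 promises capture of any non-opioid pain medication, but the form questions that admit a drug ask only about prescription medication, so over-the-counter analgesics not already listed by name are missed.

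*Protocol*

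**What the plan says.** Section 7.1 lists as a secondary endpoint: "Among subjects taking other medication, total daily dose change over time". Section 9.1 names analgesics among the medications whose dose change will be analysed.

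Section 7.2.6 sets the scope of data capture: "Physicians will confirm subjects who take any non-opioid concomitant medication for pain at baseline, or who start it during the study". The classes it names are "Nonsteroidal Anti-inflammatory Drugs (NSAIDs) and Acetaminophen, Antidepressants, Anticonvulsants, Benzodiazepines and Muscle Relaxants", and it adds: "Physicians will be asked to report the medication type and total daily dose, and any changes throughout the study". None of this is limited to prescribed supply.

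The forms are worded differently:

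- **Appendix 1, baseline.** The question that opens the drug rows asks about the "following classes of prescription medication (select all that apply".
- **Appendix 2, new medication.** The question is whether, since the last visit, the patient has started "taking any of the following classes of prescription medication (select all that apply". The row for a new drug outside the listed classes is also labelled as prescription medication.
- **Appendix 2, existing drugs outside the listed classes.** "Is your patient still taking any of these other prescription medications".
- **Appendix 2, existing named drugs.** "At last visit, you indicated that your patient was taking [baseline_visit][nsaid1_name]. Is your patient still taking this medication". This is followed by the current total mg per day of that drug, with no limit on how it was obtained.

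**The concern.** A drug enters the record only through the baseline question or the new-medication question, and both are restricted to prescription medication. The first class on each list, NSAIDs and acetaminophen, is the one where non-prescription use is most likely to matter. A site that follows the form literally would leave out analgesics that Section 7.2.6 says will be reported.

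At stake is a stated secondary endpoint. A change in recorded analgesic dose may reflect a change in where the drug comes from, or in which drug is taken, and not a change in analgesic use. The stop reasons in Appendix 2 are side effects, cost, lack of benefit, no longer needed or replaced by medical cannabis, and unknown. None covers a switch to another drug, so a substitution has no correct code and could be entered under one of the others. Unrecorded analgesic use also complicates the reading of BPI-SF pain change. A SAP cannot repair this, because the data would never have been requested.

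**Working it through.** The protocol gives no figure for this point, so the check sets the passages side by side and traces cases through the forms.

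**Assumption.** Some NSAIDs and acetaminophen can be obtained without prescription in the participating countries. The protocol does not say so.

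**Step 1: is there another route to the data?**

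- Table 1 schedules concomitant medications at baseline, at the physician-verified follow-ups and at unscheduled visits. The subject-verified follow-ups (months 1, 3, 6, 10) do not collect them, and Appendix 3 has no such item.
- The field for other drugs in Appendix 1 sits behind the prescription question and is for drugs outside the listed classes. A non-prescription NSAID does not belong there.
- Section 7.2.2 describes BPI-SF items on current treatments and relief, but the BPI as printed in Appendices 1 to 3 does not show them.

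No backstop was found.

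**Step 2: trace each case, reading the questions literally.**

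| Case | What the form records | Error |
|---|---|---|
| (a) Prescribed drug A stopped, a different over-the-counter drug B started | A stopped (-100% of its daily dose); B absent | Reduction shown whatever the true change in analgesic use |
| (b) Same drug moved from prescription to over-the-counter supply | Still taking it, with current mg per day | None |
| (c) Over-the-counter drug added to unchanged prescribed drugs | No change | Increase missed |
| (d) Over-the-counter drug used at baseline, later stopped | No change | Reduction missed |
| (e) Over-the-counter drug used at baseline, later prescribed | New start | False increase |

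**Step 3: add up the directions.** Cases (a) and (c) make the record look more favourable than the truth. Cases (d) and (e) do the opposite. Case (b) is neutral. The protocol gives no frequency for any of them, so neither a net size nor a net sign follows.

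**The case against.** The strongest reply is that the literal reading may not be how sites behave. The same list includes medical cannabis from another licensed producer, although Section 4.1 says that in Canada cannabis is authorized and the subject chooses product and producer. Acetaminophen is listed without qualification, and the drug rows ask only for a name and a daily total. Physicians are trained on the protocol and on the data system before enrolling (Section 5.2), and Section 7.2.6 says any medication. Some sites may therefore enter over-the-counter drugs. This stands as a reason not to assume that all such use is lost. It does not remove the contradiction: the form does not ask for these drugs, and if some of the 50 to 150 sites enter them and others do not, capture differs by site.

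Three stronger readings are tempting, and the protocol does not support them:

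- **That a subject who moves to the same drug over the counter is recorded as stopped.** The by-name question and its current dose item are not tied to supply, so that subject is recorded correctly.
- **That the error always favours the product.** Cases (d) and (e) err the other way. If the endpoint is read as covering only subjects recorded as taking a class at baseline, users of over-the-counter products alone fall outside it and the opposing errors shrink. Section 7.1 does not settle that reading.
- **That the overstatement can be put at a number of percentage points.** Any such figure needs a stop rate and a substitution rate, and the protocol gives neither.

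**Conclusion.** Section 7.2.6 and the forms contradict each other on which medication is recorded. Followed as written, the forms miss over-the-counter analgesics that are new, added on, or substituted for a different prescribed drug. In the substitution case the form shows the prescribed drug falling to zero and says nothing about its replacement.

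The size and net direction of the resulting error in the dose-change endpoint cannot be computed from the protocol. It would be wrong to say that the registry will report a reduction that did not happen; it can do so for individual subjects in case (a). The conclusion rests on a literal reading of the form questions and on the assumption that drugs in the NSAID/acetaminophen class are available without prescription. One secondary endpoint is affected directly; the primary endpoints are not.

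**What to change.** In Appendices 1 and 2:

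1. Reword the baseline question, the new-medication question and the items for other drugs to cover prescription or over-the-counter medication for pain, matching Section 7.2.6.
2. Add a prescription/over-the-counter tick box to each drug row in the NSAID/acetaminophen class.
3. Add a stop reason for a switch to another drug, prescription or over-the-counter.

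The alternative is to limit Section 7.2.6, the endpoint and its conclusions to prescribed medication, and to make no claim of reduced overall analgesic use. That restriction is also needed for any data already collected on the present form wording.

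The cost is a wording edit, one tick box per row in one class, and one extra response option. The downside is that over-the-counter doses rest on subject report and are less exact; the tick box lets the analysis show the two sources separately.
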